2.4.5.6 Analyses of electrocardiogram variables

The number (%) of patients with normal/abnormal ECG result during the on-treatment period will be summarized by arm (and all treated patients for Phase 1).

2.4.5.7 Analyses of other safety endpoints

A shift table of baseline ECOG PS versus best and worst ECOG PS on treatment will be provided.

The summary statistics (including number, mean, median, Q1, Q3, standard deviation, minimum and maximum) of baseline values, peak values, change from baseline and relative change from baseline will be calculated for Cytokines (TNF- α , IL-1- β , IL-4, IL-6, IFN- γ), markers of complement (C3a, C4, CH50) and serum tryptase when available.

For IAT, a summary of patients with indirect Coombs test during the on-treatment period will be provided, including number (%) of patients with:

- All tests negative.
- At least one positive test.

And among patients with at least one positive test during study treatment, number (%) of patients with:

- Negative indirect Coombs test at baseline.
- Missing indirect Coombs test at baseline.

A listing of chest x-ray results will be provided.

2.4.6 Analyses of immunogenicity variables

Immunogenicity analysis will be done separately for isatuximab and cemiplimab.

Number of evaluable patients, number (%) of pre-existing ADA and negative patients at baseline, number (%) of boosted and induced patients (either transient, persistent or indeterminate) will be reported, along with descriptive statistics of titer, by arm and overall. Prevalence and incidence will also be presented.

In addition, for positive ADA patients, time to onset, duration of ADA response, and the characterization of the immune response (transient, persistent, indeterminate) will be provided.

An individual data listing with ADA samples status (positive, negative or inconclusive), the titer if applicable, date of first/last dose, duration of exposure, study period, cycle/day, time point and date/time of sampling along with C_{trough} value of the drug will be provided for all patients.

The impact on safety and efficacy endpoints may be further explored by graphical methods or descriptively, depending on the ADA prevalence.

2.4.7 Analyses of pharmacokinetic variables

PK analysis will be done separately for isatuximab and cemiplimab.

2.4.7.1 PK parameters

2.4.7.1.1 Cycle 1

Following the first administration, individual concentrations and PK parameters of drug will be listed and summarized by descriptive statistics (such as the number of observations, arithmetic and geometric mean, median, SD, standard error (SE), coefficient of variation (CV)%, minimum, and maximum) by arm and possibly overall.

Individual and mean concentration profiles over time will be plotted by arm and possibly overall under the responsibility of Sanofi, Pharmacokinetic, Dynamic and Metabolism (PKDM), Translational Medicine and Early Development (TMED) department.

A comparison between isatuximab PK parameters (C_{max} and AUC_{0-7d}) obtained after monotherapy (control arm) and isatuximab combined treatment with cemiplimab (DL1 and DL-1 arms) based on geometric mean ratio will be provided.

2.4.7.1.2 Overall treatment: C_{trough} and C_{eoi}

C_{trough} defined as a sample collected before dosing, and in a time window of 12 to 16 days after the previous infusion for the Q2W administration, or in a time window of 6 to 8 days after the previous infusion for the QW administration will be included in the descriptive analysis irrespectively of infusion interruption. However C_{trough} drawn outside collection of time window described in the PKPD flowchart of the protocol or collected after dose deviation higher than $\pm 50\%$ from intended dose will be excluded from the analyses.

C_{eoi} collected after significant infusion interruption, drawn outside collection of time window described in the PKPD flowchart of the protocol or collected after dose deviation higher than $\pm 50\%$ from intended dose will be excluded from the analyses.

Individual C_{trough} and C_{eoi} will be listed and summarized with same descriptive statistics as above by arm and possibly overall.

Mean ($\pm SE$) of C_{trough} will be plotted over treatment phase by arm and possibly overall.

Individual C_{trough} ratio and C_{eoi} ratio (described in [Table 10](#)) will be listed and summarized by descriptive statistics by arm and possibly overall as described above.

Table 10 - C_{trough} and C_{eoI} ratio

Analyte	C _{trough}	C _{eoI}
Isatuximab	C2D1 vs C1D8	C2D1 vs C1D1
	C4D1 vs C1D8	C4D1 vs C1D1
cemiplimab	C4D1 vs C1D15 (DL1)	C4D1 vs C1D1
	C4D1 vs C2D1 (DL-1)	

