1.3 PK/PD FLOWCHART FOR ISATUXIMAB QW/Q2W + CEMIPILIMAB Q4W

1.3.1 Isatuximab QW/Q2W + cemiplimab Q4W (DL-1) - Treatment phase: Cycle 1 (Rich sampling) and Cycle 2

Procedure		Treatment Phase												
		C1							C2					
		D1			D4	D8	D15		D22	D1		D15		
Cemiplimab	IV infusion	X-----X									X----X			
	Sample RNT (h)	SOI	EOI	EOI+4h	72h	168h	336h				SOI (672h at C1D29)	EOI	336h	
	Sample Time window	[-24h,SOI]	[-5 min,EOI]	±30min	±5h	±24h					[-24h,SOI]	[-5 min,EOI]		
	PK sample ID	S00	S01	S02	S03	S04	S05 ^e				S00 ^d	S01	S02 ^e	
	ADA Sample ID ^a	AB00									AB00			
Procedure		C1							C2					
		D1			D4	D8	D15		D22	D1		D15		
			X-----X			X	X-----X		X		X----X		X	
Isatuximab	IV infusion		X-----X				X	X-----X		X		X----X		
	Sample RNT (h)	SOI		EOI	EOI+4h	72h	168h (SOI D8)	SOI	EOI	SOI	SOI		EOI	SOI
	Sample Time window		-	±10min	±30min	±5h	[-24h,SOI]	[-24h,SOI]	±10min	[-24h,SOI]		-	±10min	[-24h,SOI]
	PK sample ID ^b	P00 ^c		P01	P02	P03	P04 ^d	P05	P06	P07	P00 ^c		P01	P02
	ADA Sample ID ^b	AB00 ^c									AB00 ^c			

- a For cemiplimab ADA during treatment phase, samples to be collected every third Cycle from C5 (ie, on D1 of C5, C8, C11, C14, etc) till the last study treatment. In response to AEs of special interest, such as anaphylaxis or hypersensitivity, ADA samples closer to the event may be collected, based on the judgment of the Investigator and/or medical monitor. If isatuximab is stopped and cemiplimab treatment continues, cemiplimab ADA samples should be collected as planned per PK/PD flow-chart
- b Isatuximab PK and ADA samples to be collected each cycle till the last study treatment. However, collection can be stopped earlier upon notification from the sponsor based on the updated knowledge of isatuximab PK and immunogenicity. After FUP 90(±7) days after last IMP administration, no further ADA will be sampled even if the status is positive or inconclusive.
- c Isatuximab predose sample (SOI) may be collected at the same time as the predose sample of cemiplimab (SOI) before cemiplimab infusion start.
- d Sample (ie, T672h at C1D29 corresponding to C2D1 for cemiplimab and C1D8 T168h for isatuximab) must be collected even if the infusion planned for cemiplimab at C2D1 and/or infusion planned for isatuximab at C1D8 is not done or delayed.
- e Cemiplimab predose sample on D15 may be collected on at the same time as the predose sample of isatuximab (SOI) before isatuximab infusion start

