6.5.2 Dose delay and dose omission

Within a cycle, the treatment window is ± 1 day for each of the weekly administrations, ± 2 days for each of the Q2W administrations and ± 4 days for each of the Q4W administrations. A dose is deemed to have been delayed if the treatment is ≥ 2 days beyond the theoretical day of treatment for weekly dose, ≥ 3 days beyond the theoretical day of treatment for Q2W dose and ≥ 5 days beyond the theoretical day of treatment for Q4W dose. The reason for dose delay will be captured. Patient will receive the next infusion after recovery of the toxicity as described in [Section 6.5.3](#) and [Section 6.5.4](#). If infusion has been delayed by 2 days within a cycle, next study treatment should be administered at the planned time interval between 2 administrations (eg, Day 15 Cycle 1 administration is actually administered on Day 17, the planned Day 22 should be administered on Day 24).

Patients may have dose omission if toxicity occurs and does not recover according to following rules:

- In Cycle 1 if toxicity occurs and does not recover on the day of planned infusion or within the following 3 days, infusion of isatuximab and/or cemiplimab may be omitted.
- In Cycle 2 and beyond, if toxicity occurs and does not recover on the day of planned infusion or within the following 7 days, infusion of isatuximab and/or cemiplimab may be omitted for patient on Q2W dose schedule.

In case of consecutive dose omissions for the recovery of toxicity, following rules should be followed for restart or discontinue the treatment:

- Dose interruption (cycle delay) up to 14 days, it is per Investigator's decision to restart the treatment of cemiplimab and isatuximab.
- After dose interruption of >14 days, it is per Investigator's decision to restart the treatment of cemiplimab and isatuximab, if a clear benefit from therapy is observed and after consultation with the sponsor.

- Treatment with isatuximab and cemiplimab must be definitely discontinued if the interruption is longer than 84 days.

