1.1 STUDY DESIGN AND RANDOMIZATION

The study is conducted in 2 parts:

- The Phase 1 (lead in) part was to confirm the feasibility of the isatuximab/cemiplimab combination using 3 + 3 dose de-escalation design. The Phase 1 part of the study was completed at time of writing of this SAP. Three patients were enrolled at DL1 (isatuximab 10 mg/kg once weekly (QW) for four weeks followed by once every two weeks (Q2W) + cemiplimab 250 mg (Q2W) and no patient had DLT.
- The Phase 2 part is to further evaluate the safety, efficacy and PK of the combination versus isatuximab monotherapy. Based on the evaluation of the results from the Phase 1 part of the study, patients are randomized in the Phase 2 part of the study in 1 of the 3 arms using an interactive response technology (IRT) in a 1:1:1 ratio:
 - Arm 1 (control): isatuximab 10 mg/kg QWx4 followed by Q2W (QW/Q2W),
 - Arm 2 (DL1): isatuximab 10 mg/kg QW/Q2W + cemiplimab 250 mg Q2W,
 - Arm 3 (DL-1): isatuximab 10 mg/kg QW/Q2W + cemiplimab 250 mg Q4W.

The duration of the study for a patient will include a period for screening of up to 21 days. Patients will continue treatment until disease progression, unacceptable adverse events, consent withdrawal, or any other reason. After the last dose of study treatment (isatuximab or cemiplimab), the post-treatment follow up period include an extended safety follow-up period of 90 days, and further follow up beyond 90 days after last treatment until death or study cutoff date, whichever occur first.

A maximum of 105 patients (35 patients per arm) will be randomized in the Phase 2 randomization part. Details on study design can be found in Protocol Section 6.

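### The SAP's Ctrough rule has no window for Q4W dosing, so as written it excludes every Arm 3 cemiplimab trough and contradicts its own Table 10

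*SAP*

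**What the plan says.** SAP section 2.4.7.1.2 decides which samples enter the Ctrough description over the treatment period. A sample must precede dosing and, on a two-weekly schedule, lie "in a time window of 12 to 16 days after the previous infusion for the Q2W administration". On a weekly schedule the corresponding limits are 6 and 8 days. Any sample that meets its limits "will be included in the descriptive analysis irrespectively of infusion interruption". There is no third clause. A further sentence removes samples drawn outside the flowchart collection times or after a dose more than 50% away from the intended one.

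SAP section 2.4.7 has PK analysed separately for each drug, so the rule governs cemiplimab as well as isatuximab. SAP section 1.1 lists "Arm 3 (DL-1): isatuximab 10 mg/kg QW/Q2W + cemiplimab 250 mg Q4W" among the randomized arms. Protocol section 1.3.1 times that arm's cemiplimab sample at Cycle 2 Day 1 as 672 h after the first dose. Section 1.3.2 adds pre-dose samples on Day 1 of Cycles 3, 4 and later.

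Table 10, in the same SAP section as the rule, requires the cemiplimab Ctrough ratio "C4D1 vs C2D1 (DL-1"). The general Ctrough definitions (SAP section 2.1.6, Protocol Table 9) give no elapsed-time window, so they do not fill the gap.

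**The concern.** The two windows fit weekly and two-weekly dosing. A four-weekly trough cannot meet either of them, although one randomized arm is dosed that way. A programmer who follows the text would produce an empty Arm 3 column for cemiplimab Ctrough and could not compute the ratio that Table 10 asks for. The alternative is to choose a window once the data are in hand.

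Cemiplimab PK in combination is a secondary objective (SAP section 1.2.2), and Protocol section 4.3.2.2 gives exposure as the reason for studying two cemiplimab schedules. Repeated-dose troughs by schedule are therefore an output that readers will look for. The same definition feeds the immunogenicity-impact summaries in SAP section 2.4.7.2. A patient moved from Q2W to Q4W cemiplimab under Protocol Table 2 meets the same gap.

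**Working it through.** **1. Where the existing windows come from.** Protocol section 6.5.2 allows ± "1 day for each of the weekly administrations, ± 2 days for each of the Q2W administrations", and ±4 days for Q4W. Dosing interval plus or minus treatment window gives:

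- QW: 7 ± 1 = 6 to 8 days, which matches the SAP.
- Q2W: 14 ± 2 = 12 to 16 days, which matches the SAP.
- Q4W: 28 ± 4 = 24 to 32 days, which is absent from the SAP.

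Both stated windows are reproduced exactly. The third term of the same protocol sentence was not carried over.

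**2. Can a Q4W trough meet either window?** Nominally, 672 h / 24 = 28 days, which is in neither. Letting the interval run over 24 to 32 days, 0 of 9 whole-day values qualify. Letting both doses move by up to 4 days, with the sample drawn on time or 24 h early:

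- shortest gap: 28 − 4 − 4 − 1 = 19 days
- longest gap: 28 + 4 + 4 − 0 = 36 days
- combinations: 9 × 9 × 2 = 162, of which 0 qualify

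Even the shortest gap is 3 days beyond the 16-day limit.

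**3. Table 10.** It lists four Ctrough ratios:

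- isatuximab: C2D1 to C1D8, and C4D1 to C1D8
- cemiplimab DL1: C4D1 to C1D15
- cemiplimab DL-1: C4D1 to C2D1

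The isatuximab and DL1 samples sit at 7 or 14 days and qualify. Both terms of the DL-1 ratio are 28-day troughs, so the rule removes numerator and denominator alike.

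**4. Counting from the last infusion of either drug.** Cycle 2 Day 1 is Day 29 of Cycle 1, so 29 − 22 = 7 days after the Day 22 isatuximab infusion. Cycle 4 Day 1 is 29 − 15 = 14 days after the Cycle 3 Day 15 isatuximab infusion. Both would then pass. This reading conflicts with analysing each drug separately, and the window would no longer control time since the cemiplimab dose.

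**5. The DL-1 Day 15 cemiplimab sample.** 336 h / 24 = 14 days. With the visit windows in Protocol sections 12.4.1 and 12.4.2, the range is 13 to 15 days in Cycle 1 and 12 to 16 days later. On elapsed days alone, all of these lie inside the Q2W window.

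**6. Effect of the repair.** A window of 24 to 32 days contains the 28-day troughs and excludes the 14-day sample.

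**The case against.** The strongest defence is that the rule is incomplete and was never meant to drop Arm 3. Each window is tied to a schedule, and the separate exclusion sentence would not remove a DL-1 pre-dose sample taken in the 24 hours before the infusion. Table 10 shows that these troughs were to be kept. The SAP also handles Q4W explicitly in its exposure sections (2.4.3.1 and 2.4.3.3). This stands as evidence of intent. It does not supply a window, and the inclusion sentence is the only text that says which samples are summarized.

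A reader might go further and infer that the Day 15 sample would take the place of the true trough, because a footnote in Protocol section 1.3.1 reads "Cemiplimab predose sample on D15 may be collected on at the same time as the predose sample of isatuximab (SOI) before isatuximab infusion start". The documents do not support that as the plain reading. DL-1 has no cemiplimab dose on Day 15, the flowchart labels the sample 336 h where true pre-dose samples are marked as start of infusion, and the 12-to-16-day clause is for Q2W administration. Admission requires treating the isatuximab infusion as the cemiplimab dose and ignoring the schedule named in the clause. Table 10 names C2D1 and C4D1, so the ratio could not be affected in any case. This remains a secondary ambiguity that merits one clarifying sentence.

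A last objection concerns the width of the new window. Protocol section 6.5.2 gives ±4 days for Q4W doses, while the heading of section 12.4.2 puts Day 1 visits at ±2 days, which would give 28 ± 2 = 26 to 30. The two passages should be reconciled. The narrower range lies inside 24 to 32, so the need for a Q4W window does not depend on the outcome.

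**Conclusion.** The point holds. As written, the rule admits no cemiplimab Ctrough from Arm 3 (35 planned patients) when doses are given within the protocol's treatment windows. The by-arm summary and plot are empty for that arm, any ADA-subset summary has the same gap, and one of the four Ctrough ratios cannot be computed. The finding assumes that elapsed days are counted from the previous infusion of the drug being analysed.

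A reader might infer that Arm 3 loses its cemiplimab exposure data altogether. It does not. SAP section 2.4.7.1.1 lists and summarizes concentrations after the first administration, so the first-dose 672 h value may still be reported there. AUC0-28d is a planned DL-1 parameter in SAP section 2.1.6. Neither is governed by this rule.

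The consequence is descriptive only. Isatuximab troughs, troughs on cemiplimab Q2W dosing, safety, and the response-rate comparison do not change. It should still be corrected, because the section contradicts itself and the repair is already implied by the protocol.

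**What to change.** Make three short changes in SAP section 2.4.7.1.2:

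- Add a third inclusion window for Q4W dosing: 24 to 32 days since the last infusion, citing the 4-day Q4W window in Protocol section 6.5.2.
- State that all Ctrough windows are counted from the previous infusion of the same drug.
- State that the DL-1 Day 15 (336 h) cemiplimab sample is a mid-interval concentration and not a Ctrough.

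The Q4W window is built in the same way as the existing two. Like them, it will not keep every sample when consecutive doses shift in opposite directions. The cost is a few lines of SAP text and the matching derivation code. No new samples, dosing changes or changes to any hypothesis test are needed.

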2.4.7.2 Immunogenicity impact on PK

Immunogenicity impact on PK analysis may be explored, depending on the ADA prevalence.

A descriptive statistics of C_{trough} as described above will be provided at each cycle in the subset of negative patients by arm and possibly overall where positive or inconclusive patients will be observed.

A graphical representation of individual C_{trough} profile will be provided throughout the course of treatment by arm and possibly overall where positive or inconclusive patients will be observed. Positive patients profile will be highlighted (eg, color or bold) and the concentration of the administered drug at the same time as ADA positive result will be notified.

2.4.8 Analyses of Biomarker variables

2.4.8.1 Genetic variables

Summary of BOR will be provided for the following patients:

- High risk cytogenetic markers (del17p and/or t(4;14) and/or t(14;16)).
- FcGR3A types: F/F, F/V, V/V and missing.
- HLA and KIR genotypes including:
 - HLA-B BW4-80lle+ and KIR3DL1+ vs HLA-B BW4-80lle- or KIR3DL1-,
 - KIR3DS1- vs KIR3DS1+.

2.4.8.2 Other variables

Graphs showing ORR/non-responder rate by biomarker levels will be provided for the following parameters at baseline:

- CD38 mRNA.
- Immune cell level (B-cell, T-cell and NK-cell subsets respectively in blood and bone marrow samples).

Bone marrow and blood samples will be collected for the following biomarker analyses:

- Correlation of immunophenotype in bone marrow and/or peripheral blood with parameters of clinical response. Blast cells and immune cell populations (including MDSC cell, T-cell, NK-cell subsets and Treg/CD8 effector ratio) will be characterized by multiparametric flow cytometry analysis on the expression of cell surface markers. The proportion of cells positive for a given marker or set of markers (eg, regulatory T cells [Tregs]) will be correlated with response to SAR650984. Bone marrow aspirate and blood will be collected at baseline and Day 1 of Cycle 3 and blood samples only will be collected at EOT.
- Whenever possible, PD-L1 expression in malignant plasma and immune cells will be determined and correlated with clinical response. Access to archival bone marrow biopsy material will be requested at screening and if available, retrospective expression analysis will be performed by IHC assay.
- Correlation of adaptive immune response (TCR repertoire profiling) with parameters of clinical response. Blood and bone marrow samples will be collected at screening, D1 of Cycle 3 (blood only) and at CR.
- Correlation of adaptive immune response (humoral and cellular immune responses to myeloma-related tumor antigens) with parameters of clinical response. Blood will be collected prior to pre-medication and IMP administration on D1 of Cycle 1, Cycle 2, Cycle 4, Cycle 7 and Cycle 10 and in disease progression patients at EOT. Humoral response will be assessed in all sites. Cellular response will be assessed in patients at selected sites.

Additional analysis, not specified in the protocol but related to the drug action and/or effect of isatuximab/cemiplimab, may be conducted on remaining samples pending evolving literature.

2.4.8.3 Potential interference of isatuximab in the M protein assessment

Number (%) of patients with M protein interference and with potential impact on the BOR will be explored.

2.4.9 Analyses of quality of life variables

Not applicable as no quality of life variable is collected.

2.4.10 Further therapy after discontinuation of investigational medicinal product administration during the study

Further therapies will be descriptively summarized by arm and overall.

2.5 DATA HANDLING CONVENTIONS

2.5.1 General conventions

The following formulas will be used for computation of parameters.

Creatinine clearance (eGFR) using the equation of MDRD formula:

$$\text{GFR} = 175 \times (\text{Scr})^{-1.154} \times (\text{Age})^{-0.203} \times (0.742 \text{ if Female}) \times (1.212 \text{ if African American})$$

with serum creatinine in mg/dL and age in year.

Corrected calcium formula:

Corrected Calcium (mmol/L) = Serum Calcium (in mmol/L) + 0.8*0.25 (4 - serum albumin [in g/dL])

2.5.2 Data handling conventions for secondary efficacy variables

Not applicable.

2.5.3 Missing data

The analyses and summaries of continuous and categorical variables will be based on observed data only. Percentages will be calculated using as the denominator the number of patients with a non-missing observation in the considered population. When relevant, the number of patients with missing data will be presented.

When incomplete or missing dates were found in the eCRF, attempts were made to retrieve the complete date, especially for dates within the month prior to first dose. However, if some dates remain incomplete, the following rules will be applied:

Handling of disease characteristics missing/partial dates (if not otherwise specified below)

- If the day is missing, it will be imputed to be 1.
- If the month is missing, it will be imputed to be 1 (only for medical history variables).
- If the year is missing, no imputation will be performed.

Handling of medication (other than anticancer treatment) missing/partial dates

No imputation of medication start/end dates or times will be performed. If a medication date is missing or partially missing and it cannot be determined whether it was taken prior or concomitantly, it will be considered a prior, concomitant, and post-treatment medication.

Handling of post anti-myeloma treatment missing/partial dates

For post anti-myeloma treatments, if the anticancer treatment start date is missing, it will be imputed as follows:

- If the medication start day and month are missing and the medication start year is the same as treatment end year, the medication start date will be set equal to treatment end date + 1.
- If the medication start day and month are missing and the medication start year is after the treatment end year, the medication start day and month will each be set to 01.
- If the medication start day is missing and medication start year and month is the same as the treatment end year and month, the medication start day will be set equal to the treatment end day + 1.
- If the medication start day is missing and medication start month is before the treatment end month and the medication start year is the same as treatment end year, the medication start day will be set to 01.
- If the medication start day is missing and the medication start month is after the treatment end month and the medication start year is the same as treatment end year, the medication start day will be set to 01.
- If the medication start day is missing and the medication start month is not missing and the medication start year is after the treatment end year, the medication start day will be set to 01.
- If the medication start day, start month and start year is missing, the medication start date will be set equal to the treatment end date + 1.

No imputation will be done for the missing/partial end date.

Handling of adverse events with missing or partial date of onset

Missing or partial adverse event onset dates (occurrence or becoming serious) will be imputed so that if the partial adverse event onset date information or visit number does not indicate that the adverse event started prior to or after treatment, the adverse event will be classified as treatment-emergent. In case of AEs worsening during the study, the emergence will also be based on the cycle of worsening. No imputation of adverse event end dates will be performed. These data imputations are for categorization purpose only and will not be used in listings. No imputation is planned for date of adverse event resolution.

Handling of death with missing or partial date of death

The imputation for missing or partial death date will proceed as follows:

- If the death day is missing and the death month and year are the same as the last month and year the patient was last known to be alive, the death day will be set equal to the last day the patient was known to be alive + 1.
- If the death day is missing and the death month is after the month the patient was last known to be alive and the death year is the same as the year the patient was last known to be alive, the death day will be set to 01.

- If the death day and month are missing and the death year is the same as the year the patient was last known to be alive, the death date will be set equal to the date the patient was last known to be alive + 1.
- If the death day and month are missing and the death year is after the year the patient was last known to be alive, the death day and month will both be set to 01.

If the date the patient was last known to be alive is partial or missing, no imputation for missing or partial death date will be performed. The last date the patient was known to be alive is the last of: date of last dose, date of last visit performed (when the patient is known to be alive according to subject vital status), date of last laboratory assessment, date of last vital signs.

Handling of adverse events with missing grade

If the grade is missing for one of the treatment emergent occurrences of an AE, the maximal severity on the remaining occurrences will be considered. If the severity is missing for all the occurrences, no imputation will be done and missing grades will be summarized in the “all grades” category.

Handling of missing assessment of relationship of adverse events to investigational medicinal product

If the assessment of the relationship to study treatment (isatuximab or cemiplimab) is missing, then the relationship to isatuximab/cemiplimab has to be assumed and the AE considered as such in the frequency tables of possibly related AEs, but no imputation will be done at the data level. No imputation will be done for relationship to NMIP.

Handling of parameters expressed as inequality or approximation

For some parameters (such as laboratory parameters), if the value is expressed as “<xx”, “≤xx”, half of the numeric portion of the entry or limit of quantification will be used in calculations.

Handling of missing date/time in duration of infusion calculation

When both cemiplimab and isatuximab are given to a patient on the same visit:

- Missing cemiplimab end date/time will be imputed by isatuximab start date/time (if available).
- Missing isatuximab start date/time will be imputed by cemiplimab end date/time (if available).

Other types of missing date/time will not be imputed, and data will be excluded from the analysis of duration of infusion.

